#### **10.3.** Concomitant and Other Medications

Association of concomitant medications with treatment and coding of concomitant medications is described in Section 7.7. Concomitant medications will be summarized by treatment and WHO preferred name for Part 1 and for the entire study period. Multiple medication use (by preferred name) will be counted once only per subject. Concomitant medications started more than 30 days post last dose will not be included in summary displays but will be listed.

Concomitant medications that were used for HAE-related indications will also be summarized. separately for Part 1 and for the entire study period.

All medication data will be listed.

#### 10.3.1. Missing and Partial Concomitant and Other Medication Start and Stop Dates

See Section 6.8.3.

#### **10.4.** Laboratory Data

The following endpoint is a Part 1 safety endpoint and a primary endpoint for Parts 2 and 3:

• Number and proportion of subjects who experience a treatment-emergent Grade 3 or 4 laboratory abnormality

A listing of clinical laboratory evaluations is provided in the Protocol, Section 11.2.6.

Clinical laboratory assessments and corresponding changes from baseline will be summarized for each laboratory panel by treatment group and visit. Laboratory abnormalities will be graded according to the DMID Adult Toxicity Table (publish date: November 2007; see Protocol Appendix 16.1). Any graded abnormality that occurs following the initiation of study drug and represents at least 1-grade increase from the baseline assessment is defined as treatment emergent.

Urinalysis results will be summarized by treatment and visit and listed by subject and treatment.

The number and percentage of subjects experiencing treatment-emergent graded toxicities will be summarized. Treatment-emergent Grade 3 or 4 laboratory abnormalities will be summarized separately. Laboratory toxicity shifts from baseline to worst postbaseline assessments will be summarized.

The number and percentage of subjects who have post-baseline elevations in liver transaminase (alanine aminotransferase [ALT] or aspartate aminotransferase [AST]) or bilirubin abnormalities in relation to fold above the upper limit of normal will be summarized according to the FDA's Premarketing Clinical Evaluation on Drug-Induced Liver Injury Guidance for Industry (DHHS 2009).

The following categories of abnormal hepatic laboratory values will be evaluated for any occurrence among all post baseline assessments (where "and" indicates elevations occurring at the same visit). Within each treatment group and laboratory parameter grouping, a subject may be counted once per elevation criteria using the worst-case result. That is, a subject with a worst-case ALT elevation  $>3 \times$  the upper limit of normal (ULN) for a given treatment group would be counted once in the ALT  $> 1.5 \times$  ULN category and once in the ALT  $> 3 \times$  ULN category, regardless of how many ALT elevations the subject had that met the  $> 3 \times$  ULN and  $> 1.5 \times$  ULN elevation criteria.

- ALT and/or AST >  $3 \times$  ULN and total bilirubin > 1.5 or  $2 \times$  ULN
- AST > 1.5, 3, 5, 10, and 20 × ULN
- ALT > 1.5, 3, 5, 10, and 20 × ULN
- Total bilirubin  $> 1, 1.5, \text{ or } 2 \times \text{ULN}$
- Alkaline phosphatase (ALP)  $> 1.5 \times ULN$

Profiles of liver enzymes and bilirubin over time will be graphically displayed for subjects with any Grade 3 or 4 abnormality in these analytes. In addition, a listing of all liver function test (ALT, AST, bilirubin, ALP, gamma-glutamyl transferase) results for subjects experiencing a treatment-emergent Grade 3 or 4 liver function test will be provided.

In addition, a Hy's law plot, a shift plot showing liver safety panel tests over time (baseline vs. on-study), and distribution plots of ALT, AST, ALP, bilirubin, cholesterol, and triglycerides over time will be produced using the format recommended by the FDA/Industry/Academia Safety Graphics working group (https://www.ctspedia.org/do/view/CTSpedia/StatGraphHome). The plots to be included are the scatter plot of maximum transaminase versus maximum bilirubin, the liver test safety panel over time and the distribution of ALT by time and treatment. The distribution plots for AST, ALP, bilirubin, cholesterol and triglycerides will use the same format as is used for ALT.

Separate Kaplan-Meier plots of time to event for a Grade 3 or higher ALT, AST, or bilirubin will be produced.

A listing of adverse events of nausea, vomiting, anorexia, abdominal pain, or fatigue occurring within 24 hours of an elevation of >3xULN for AST or ALT will be produced.

#### **10.4.1.** Prior Androgen Use and Liver Function Test Abnormalities

The summary display of abnormal hepatic laboratory values will be repeated by prior use of androgens (yes/no) at any time in the past based on medical history. Detailed listings of prior androgen use will be provided for subjects with any elevation in the indicated categories.

#### **10.4.2.** Complement Factors and HAE Diagnosis

Laboratory results related to HAE diagnosis, including complement factors C1-INHAg, C1-INHf, C3, and C4 will be included in summaries of laboratory data. Criteria used to confirm diagnosis of HAE Type 1 or 2 will be summarized and listed as described in Section 7.4.

#### 10.4.3. Laboratory Assessments for Rash

For subjects with rash, peripheral blood mononuclear cells (PBMCs) will be collected for analysis of possible drug-specific immune responses and possible drug-responsive T-cells. The data from PBMC analysis, if collected, will be listed.

Other laboratory assessments taken at the time of a rash, including clinical chemistry, hematology with differential, C3 level, and urine eosinophils will be included in laboratory listings.

#### 10.5. Pregnancy

A listing of pregnancy test results will be provided.

#### 10.6. Vital Signs

Vital signs (systolic and diastolic blood pressure, pulse rate, temperature, and respiratory rate) and body weight and corresponding changes from baseline will be summarized by treatment group and visit using descriptive statistics. These data will be listed by subject, treatment, and visit.

Distribution plots of systolic and diastolic blood pressure over time will be produced using the format recommended by the FDA/Industry/Academia Safety Graphics working group (https://www.ctspedia.org/do/view/CTSpedia/StatGraphHome). The graph format to be used is the same as the graph provided for the distribution of ALT by time and treatment.

#### **10.7. 12-lead Electrocardiograms**

Baseline (predose) and Week 24 ECGs will be obtained in triplicate (ie, 3 separate readings) at 1- to 5-minute intervals, with baseline values calculated from an average of the 3 readings. All other ECGs will be single assessments.

An ECG should be repeated for a change from baseline in corrected QT interval using Fridericia's method (QTcF) > 60 msec or a QTcF interval > 500 msec.

ECGs and corresponding changes from baseline will be summarized by treatment group and visit using descriptive statistics.

ECG findings will be summarized.

The change from baseline in QTcF will be determined by routine ECGs. At each time point where ECGs are analyzed, an individual subject's change from baseline will be calculated as:

 $\Delta ik = (QTcF \text{ for Subject i at Time Point } k - Baseline QTcF)$ 

QTcF measurements will be the average of triplicate ECGs at baseline and Week 24 and single values at all other time points.

A distribution plot of QTcF over time will be produced using the format recommended by the FDA/Industry/Academia Safety Graphics working group

(https://www.ctspedia.org/do/view/CTSpedia/StatGraphHome). The graph format to be used is the same as the graph provided for the distribution of ALT by time and treatment.

For routine ECGs, the number and proportion of subjects with  $QTcF \le 450$ , > 450 to  $\le 480$ , > 480 to  $\le 500$ , and > 500 msec; or changes of  $\le 30$ , > 30 to  $\le 60$ , or > 60 msec will be summarized. Unscheduled ECG results will be included in this summary table.

All ECG values and findings will be listed by subject, treatment, and visit.

#### **10.8.** Physical Examination

A full physical examination is conducted at Screening, Baseline, and at Week 24. Symptom-directed physicals are done at all other study visits except Week 2 and Week 26. Physical examination data will be listed by subject and treatment.

#### 10.9. Study Termination Status

Study termination status will be presented on the subject disposition table.

## 11. PHARMACOKINETICS

Analyses of concentration data will be performed using the safety population. PK concentration data will be listed by subject, treatment, day, and time for Part 1 and this will be repeated for the entire study period for the analysis at the end of the study. Note that PK concentration data collected at each visit will not be summarized by visit as the timings of PK data collected was not pre-specified.

The following summary displays will be produced:

- Summary of number and percentage of collected samples  $> 4 \times$  half-maximal effective concentration (EC50),  $> 6 \times$  EC50, and  $> 8 \times$  EC50 at each visit and overall
- Summary of number and percentage of samples within a subject >  $4 \times EC_{50}$ , >  $6 \times EC_{50}$ , and >  $8 \times EC_{50}$

The value of  $EC_{50}$  used will be 9 ng/mL.

## **12. PHARMACODYNAMICS**

Analyses of PD data will be performed using the PD population. Plasma kallikrein inhibition data will be expressed as percent inhibition compared to subject baseline activity (%KKI). The formula for percent inhibition is:

 $\% KKI = -\frac{postbaseline \ value - baseline \ value}{baseline \ value}$ 

where the values are the amidolytic activity (%) at each time point. Multiple assessments of amidolytic activity from samples at a single time point will be handled as described in Section 6.7.4.

%KKI data will be listed by subject, treatment, day, and time. This analysis will be conducted for Part 1 and then repeated for the entire study period for the analysis at the end of the study.

The following summary displays will be produced:

- Summary of number and percentage of collected samples with > 50% and > 80% inhibition at each visit and overall
- Summary of number and percentage of samples within a subject with > 50% and > 80% inhibition

#### **13. PHARMACOKINETIC/PHARMACODYNAMIC ANALYSES**

A scatter plot of %KKI (y-axis) by PK concentration/4 (x-axis) will be produced at the time of the Part 1 analysis and for the entire study period at the time of the analysis at the end of the study, using the PK/PD population. Note the division by 4 of the concentration corrects for the dilution of the plasma required for the PD assay.

#### 14. PHARMACOGENETICS

Pharmacogenetic samples will be collected on all subjects who are willing to participate in pharmacogenetic testing. If a decision is made to analyze the samples and conduct a statistical analysis of the results, the statistical analysis will be the subject of a separate SAP.

Results of human leukocyte antigen typing will be evaluated in a separate cross-study analysis.

#### **15. CHANGES FROM PROTOCOL-SPECIFIED ANALYSES**

Changes from protocol-specified analyses include:

- For Part 1 analyses, the protocol says efficacy displays will be generally be performed over the entire dosing period beginning on Day 1 and effective dosing period beginning on Day 8. In the SAP, a reduced number of displays have been selected for analysis over the effective dosing period.
- In the protocol, the PP population was originally defined as a subset of the ITT population. It has been redefined in the SAP as a subset of the safety population.
- Due to an error in the IXRS equation, the baseline attack rate for screening for purposes of stratification was slightly larger than it should have been because the denominator did not include the "+1"; ie, the number of days in screening was underestimated by 1 day. For analysis purposes, the baseline attack rate is recalculated using the intended equation for baseline attack rate as shown in Section 6.6.1.
- Clarified that Part 1 ends at the time of first dose for Part 2.
- Increased the sample size per group from 32 to 40 to account for potential dropout. Initial sample size estimates did not allow for any subject dropout.

• Due to rapid enrollment and the timing of planned sample size re-estimation when 50% of subjects reach Week 24, the planned sample size re-estimation was not conducted.

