# Part 1 (24-week evaluation of blinded efficacy and safety data)

Subjects with HAE Type 1 or 2 will be eligible for the study following assessment of data obtained from screening procedures, including demonstration of a minimum number of attacks

documented during a prospective run-in period of 2 to 8 weeks from the date of the screening visit.

Approximately 96 treatment-eligible subjects will receive study drug (BCX7353 or placebo) in Part 1 of the study based on randomization in a 1:1:1 ratio into 1 of 3 treatment groups:

Group 1 (N = 32): BCX7353 110 mg administered orally QD for 24 weeks

Group 2 (N = 32): BCX7353 150 mg administered orally QD for 24 weeks

Group 3 (N = 32): Placebo administered orally QD for 24 weeks

Enrollment into treatment groups will be stratified by the baseline HAE attack rate ( $\geq 2$  attacks/month vs. < 2 attacks/month).

Qualifying attacks for eligibility determination are characterized as follows:

- The attacks must occur during the run-in period of 56 consecutive days, starting on the day of the screening visit
- The attacks are unique, defined as an attack that does not begin within 48 hours of the end of a previous attack.
- The attacks must have either been treated, required medical attention, or be documented to cause functional impairment, based on the subject's entry in the electronic diary (e-diary). Functional impairment is defined as the subject not being able to perform his or her daily activities without restriction (ie, subject records that he/she is at least slightly restricted in daily activities during the HAE attack).
- The attacks must include symptoms of swelling. Symptoms of swelling, in addition to visible swelling, may also include symptoms in the oropharyngeal or abdominal regions, which are indicative of internal swelling.
- The attacks are otherwise confirmed by the Investigator to be HAE attacks.

Once the subject records 2 such attacks, he or she may be randomized to study drug beginning on or after Day 28 of the run-in period; subjects who have at least 3 such attacks may be randomized to study drug beginning on or after Day 14 of the run-in period. A study schematic can be found in Figure 1.

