Beginning at screening and through the Week 48 visit, details of acute attacks of angioedema will be recorded in an electronic diary (e-diary). Attacks will be treated in accordance with the subject's normal standard of care. Within approximately 2 business days of the end of each attack that occurs from the screening visit through the Week 48 visit, subjects will be contacted by the Investigator (or appropriately trained designee) to discuss the clinical characteristics of the attack, any questions on the entered data or to gain additional attack details not included in the e-diary that the Investigator deems important to clinically evaluate the event, as applicable. This information, in conjunction with the e-diary record, will be used by the Investigator to verify or reject the event recorded in the diary as an HAE attack. All Investigator-confirmed attacks of HAE must include symptoms of swelling; prodromal symptoms in the absence of swelling are not considered HAE attacks, regardless of treatment. Symptoms of swelling, in addition to visible swelling, may also include symptoms in the oropharyngeal or abdominal regions, which are indicative of internal swelling.

The main study will be comprised of adult subjects ( $\geq 18$  years of age); a substudy in participating regions will allow adolescent subjects ( $\geq 12$  to 17 years of age) to enroll. Main study and substudy subjects will be randomized via a separate randomization scheme; however, study-mandated procedures will be identical, and the analyses will include all subjects who participate in the study.

Study visits in Part 1 will occur at screening, baseline and Weeks 2, 4, 8, 12, 18 and 24. The primary efficacy analysis will occur after the last subject completes the Week 24 visit and will include all data through Week 24. Subject treatment will remain blinded to the subjects, site staff, and Sponsor staff who interact with sites on a regular basis during Part 2.

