#### 4.4.1. Part 1 Randomization

Approximately 96 subjects will be randomized in a 1:1:1 (active:active:placebo) ratio to 1 of the following treatments in Part 1:

- Group 1: BCX7353 110 mg administered orally QD for 24 weeks
- Group 2: BCX7353 150 mg administered orally QD for 24 weeks
- Group 3: Placebo administered orally QD for 24 weeks

Enrollment into treatment groups will be stratified by the site-calculated baseline HAE attack rate ( $\geq 2$  attacks/month vs. < 2 attacks/month). The site-calculated baseline attack rate must have been provided during randomization and was to be calculated as:

Number of HAE attacks meeting baseline criteria from Screening to Randomization × 28 Randomization Date – Screening Date + 1

HAE attacks to be utilized in calculation of the baseline attack rate must meet the following criteria:

- The attacks must be unique, which is defined as an attack that does not begin within 48 hours of the end of the previous attack.
- The attacks must have either been treated, required medical attention, or have been documented to cause functional impairment based on subject entry in the e-diary. Functional impairment is defined as the subject being unable to perform daily activities without restriction (ie, subject records that he/she is at least slightly restricted in daily activities during the HAE attack).
- The attacks must include symptoms of swelling. Symptoms of swelling, in addition to visible swelling, may also include symptoms in the oropharyngeal or abdominal regions, which are indicative of internal swelling.
- The attacks must be confirmed by the Investigator to be HAE attacks. Subjects will be contacted within 2 business days of the attack to discuss the attack and to resolve any Investigator queries on the entered data in the e-diary, as applicable.

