## 6.6.1. Baseline Attack Rate

Enrollment into treatment groups is stratified by the baseline HAE attack rate as determined by the IXRS system based on the number of attacks and duration of screening as input by the sites ( $\geq 2$  attacks/month vs. < 2 attacks/month). For analysis purposes, the baseline attack rate will be calculated from the diary data and expressed as attacks per month where 1 month = 28 days as follows:

Number of HAE attacks meeting baseline criteria from Screening to First Dose Date/time × 28

Date of First Dose – Screening Date + 1

Criteria that must be met for attacks to qualify for confirmation by the Investigator during the baseline period are provided in Section 4.1.

Baseline attack rate will be included in statistical models as appropriate.

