# 8.6. Analysis of the Primary Efficacy Endpoint

## 8.6.1. Primary Efficacy Analysis

The primary efficacy endpoint for Part 1 of the study is the rate of investigator-confirmed HAE attacks during dosing in the entire 24-week treatment period during Part 1 (Day 1 to first dose of Part 2). The first dose in Part 2 is expected on Day 169. The primary efficacy analysis will be produced using the ITT population. The estimand will be based on data from subjects who are on study treatment and this analysis will not include data post treatment discontinuation.

The number of investigator-confirmed HAE attacks for Part 1 will be analyzed by treatment group using appropriate descriptive statistics for the confirmed attack rate (expressed as attacks/month) based on the 24-week dosing period or until study treatment discontinuation, if applicable. An additional summary of confirmed attack rate by month, including change from baseline attack rate and percentage change from baseline attack rate by month, will be produced. The primary efficacy analysis will be conducted using Part 1 data and the primary efficacy endpoints will be summarized and listed by Part 1 treatment group.

The attack rate and the treatment comparisons between each BCX7353 dose and placebo in the rate of investigator-confirmed HAE attacks during the Part 1 dosing period will be analyzed using a Poisson regression model. The number of investigator-confirmed attacks will be included as the dependent variable, the treatment will be included as a fixed effect, the stratification variable (baseline attack rate) will be included as a covariate and the logarithm of duration on treatment will be included as an offset variable. The estimated rate of attack for each treatment group, the treatment differences expressed as the attack rate ratio (BCX7353 over placebo rate ratio) and their associated 95% confidence intervals (CIs) will be provided from the Poisson regression model. The percentage reduction from placebo will be calculated for each dose as:

Rate reduction = 
$$1 - \text{attack rate ratio} = 1 - \frac{R_A}{R_P}$$

Where  $R_P$  is the estimated attack rate for Placebo treatment and  $R_A$  is the estimated attack rate for Active treatment.

Example SAS pseudo-code for the Poisson regression analysis is as follows:

```
proc genmod data = datasetname;
class trt01p catblatk/param=glm;
model icattacks = trt01p catblatk /dist=poisson link=log offset=logdurtrt;
run;
```

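### The primary attack-rate model adjusts for a recalculated attack-rate category instead of the stratum used to randomise, and has no term for the separate adolescent scheme; little bias is expected, and the fix is cheap

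*SAP*

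**What the plan says.** **How treatment was allocated.** SAP Section 4.4.1: "Enrollment into treatment groups will be stratified by the site-calculated baseline HAE attack rate", cut at 2 attacks per month, with the denominator "Randomization Date – Screening Date + 1". Section 6.6.1 describes the stratum "as determined by the IXRS system based on the number of attacks and duration of screening as input by the sites". Section 15 discloses that "the baseline attack rate for screening for purposes of stratification was slightly larger than it should have been", because the IXRS equation left out the +1 and so "the number of days in screening was underestimated by 1 day". Section 4.1 adds a second grouping: "Main study and substudy subjects will be randomized via a separate randomization scheme". Both groups are pooled in the analyses.

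**How the data are analysed.** Section 6.6.1 recalculates the baseline rate from diary data, up to first dose, with the +1. Section 6.6.2 defines the categorised rate from that calculated rate. The example code in Section 8.6.1 reads "model icattacks = trt01p catblatk /dist=poisson link=log offset=logdurtrt".

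The prose of Section 8.6.1 calls the covariate the stratification variable. The statistical methods summary at the front of the SAP calls it only the baseline attack rate and does not say whether it is categorical. The SAP does not define catblatk. Section 6.6.2 holds the only categorised rate that the SAP defines for analysis.

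**What is not planned.** No model term represents the adult/adolescent scheme; for efficacy, age group appears only as a subgroup (Section 8.4). None of the sensitivity analyses in Section 8.6.2 uses the stratum as randomised.

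**The concern.** Stratified randomisation balances the arms within the groups actually used to allocate. The usual practice is to carry those groups into the model, so that the standard errors reflect the design and nobody can argue later about which version of the stratum was chosen. Here the allocated stratum and the modelled category differ in three ways: the +1, the end date (randomisation or first dose) and the data source (site entry or diary). The adolescent scheme is not carried into the model at all.

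The cut-off of 2 per month also lies close to the eligibility rule. A subject with two qualifying attacks becomes eligible at about the time when the rate passes through 2: "he or she may be randomized to study drug beginning on or after Day 28 of the run-in period". Boundary subjects may therefore not be rare. At stake are a clean match between design and analysis and an unambiguous primary model. A further question is whether a two-level covariate makes good use of the baseline attack rate.

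**Working it through.** **The plan's own statement.** The SAP gives no figure for reclassification. It says only that the IXRS rate was slightly too large because screening was one day short. Let D = randomisation date − screening date, and k = number of qualifying attacks. Then:

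- IXRS rate = 28k/D
- intended rate = 28k/(D+1)
- relative excess = (D+1)/D − 1 = 1/D, which is 7.1% at D = 14, 3.6% at D = 28 and 1.8% at D = 56

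This agrees with Section 15. The 94% power in Section 4.3.1 reproduces as 94.7% (two-sample t test, 32 per arm, difference 0.5, SD 0.55), but it does not depend on this point.

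**Who changes category.** Assume equal attack counts in both sources.

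- IXRS category is at least 2 when 28k/D ≥ 2, that is D ≤ 14k.
- Recalculated category is at least 2 when 28k/(D+L+1) ≥ 2, that is D ≤ 14k − 1 − L, where L is the number of days from randomisation to first dose.

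With L = 0 the category changes only at D = 14k, always from at least 2 (IXRS) to below 2 (analysis):

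| k | D | IXRS rate | Recalculated rate |
|---|---|---|---|
| 2 | 28 | 56/28 = 2.00 | 56/29 = 1.93 |
| 3 | 42 | 84/42 = 2.00 | 84/43 = 1.95 |
| 4 | 56 | 112/56 = 2.00 | 112/57 = 1.96 |
| 5 | 70 | 140/70 = 2.00 | 140/71 = 1.97 |

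With L = 1, which the randomisation footnote to Table 2 allows for sites with a centralised pharmacy, D = 14k − 1 is added: (k, D) = (2, 27), (3, 41), (4, 55), (5, 69). Differences between site entry and diary come on top and cannot be computed from the documents.

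**Is the earliest eligible day a boundary day?** Section 4.1 starts the run-in on the day of the screening visit, so Day 28 is D = 27. With same-day dosing the rates are 56/27 = 2.07 and 56/28 = 2.00, both at least 2, and nothing changes. With first dose a day later the analysis rate is 56/29 = 1.93 and the category does change.

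**How many subjects.** This needs attack rates and visit timing that the documents do not give. The assumption is gamma-Poisson rates with means of 1.5 to 3.5 per month.

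- Randomisation spread over 0 to 14 days after eligibility: 2% to 4% reclassified.
- Randomisation in whole weeks from screening: 19% to 29%.
- Randomisation on the earliest day, taken as D = 28 for two-attack subjects: 18% to 28%. On the Section 4.1 day count this case does not arise with same-day dosing.

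**Effect on the result, unfavourable timing.** Illustrative simulation: 800 runs, 40 per arm, mean 3 attacks per month, 7% adolescents with a rate 1.3 times that of adults, whole-week visits, about 21% reclassified. Rejection rates are from a negative binomial fit with dispersion fixed at 0.35.

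| Adjustment | Mean rate ratio (true 0.6) | SD of log ratio (true 0.6) | Rejection under null | Power |
|---|---|---|---|---|
| Recalculated category | 0.597 | 0.136 | 3.2% | 95.1% |
| IXRS stratum | 0.596 | 0.146 | 4.8% | 93.9% |
| IXRS stratum + scheme | 0.595 | 0.146 | 5.0% | 93.8% |

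The Monte Carlo standard error at 5% is √(0.05 × 0.95/800) = 0.8 percentage points. The estimate does not move. Exchanging one category for the other does not improve precision by itself: the spread is 0.146/0.136 = 1.07 times as large with the IXRS stratum.

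**Effect of a continuous baseline rate.** A second illustrative simulation, with about 2% reclassified and quasi-Poisson standard errors, again showed almost no effect of the stratum change or the scheme term. Adding the Section 6.6.1 rate as a continuous covariate cut the standard error by about 8% and raised power from about 83% to 88%. The two figures agree: 83% power corresponds to an expected z of 1.96 + 0.95 = 2.91; 2.91/0.92 = 3.17; and 3.17 − 1.96 = 1.21, or about 88% to 89%.

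**The case against.** The strongest reply is that the SAP made an open and reasonable choice. Section 15 states the IXRS error, its direction, its size and the remedy. The model still adjusts for the stratification factor at the same cut, and the corrected value is arguably the better measure of baseline disease activity. In the whole-week simulation it gave a slightly smaller spread and no excess of false positives. The number of adolescents is not stated, so the value of a scheme term cannot be shown. The IXRS stratum and the continuous rate also overlap.

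Most of this stands, and it limits the point to specification and efficiency. It does not remove two facts: the planned model does not contain the groups used to allocate, and the SAP does not settle which of three covariates (IXRS stratum, recalculated category or continuous rate) is meant.

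A reader might infer more than the documents support:

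- *That the model ignores stratification altogether.* It does not; it holds a close, corrected version of the attack-rate stratum.
- *That the earliest randomisation day for two-attack subjects is itself a boundary day.* On the Section 4.1 day count it is not, unless first dose follows a day later.
- *That the treatment estimate is biased or the test too liberal.* The simulations show neither effect from this source. Plain Poisson fits rejected a true null in 47% to 50% of the whole-week runs, but for all three adjustments alike. That comes from the assumed over-dispersion, a separate matter for which Section 8.6.1 plans a negative binomial check.

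**Conclusion.** The point holds as a worthwhile refinement and does not threaten the result. The primary model adjusts for a recalculated category instead of the allocated stratum and leaves out the adolescent scheme. The two categories differ only for subjects near exactly 2 attacks per month, apart from any site-entry/diary discrepancies. The expected effect on the rate ratio is in the third decimal place (0.595 to 0.597 at a true 0.6).

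The useful gain comes mainly from entering the baseline rate as a continuous covariate, about 8% off the standard error in one simulated setting. Matching the model to the randomisation is a smaller benefit of good order.

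This rests on assumed attack rates, visit timing and adolescent share; on reading catblatk as the Section 6.6.2 category, which is an inference; and on no large disagreement between site entries and diaries. The protocol supplied is for Study BCX7353-202, so the model wording in the Study BCX7353-302 protocol could not be checked.

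**What to change.** In Section 8.6.1, before Part 1 is unblinded:

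1. Define the attack-rate covariate explicitly (source, dates and form), and make the prose, the example code and the front summary agree.
2. Fit the IXRS stratum as randomised and a main/substudy indicator as class effects, with the Section 6.6.1 baseline rate as a continuous covariate, preferably on the log scale to match the log link. Eligibility requires at least two qualifying attacks, so the logarithm should exist; state a rule for any exception.
3. Keep the recalculated category for description and subgroups and, if wanted, as a sensitivity analysis in Section 8.6.2.
4. Fix a rule, before unblinding, for dropping the scheme indicator if very few adolescents enrol.

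Do not exchange the category for the IXRS stratum without adding the continuous rate, because in the whole-week simulation the exchange alone gave up a little precision.

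The cost is a change to the model statement on data already held: one term is replaced by three, a net two degrees of freedom, with some overlap between the stratum and the continuous rate. No new data or change in sample size is needed.
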